Post Authorization Safety Study (PASS) Information

Acronym/Title	S afety and E ffectiveness of R ivaroxaban and A pixaban compared to warfarin in non-valvular atrial fibrillation patients in the routine clinical practice in the UK SiERRA UK
Protocol version and date	v 1.0, 12 Nov 2018
IMPACT study number	20343
Study type / Study phase	Observational, Phase IV PASS Joint PASS:  YES  NO
EU PAS register number	Study not yet registered
Active substance	B01A F DIRECT FACTOR Xa INHIBITORS (B01A F01 RIVAROXABAN, B01A F02 APIXABAN) and B01A A03 WARFARIN
Medicinal product	Xarelto (Rivaroxaban), Eliquis (Apixaban) and Warfarin
Product reference	EU/1/08/472/001-041
Procedure number	EMEA/H/C/00944
Comparator / Reference therapy	Warfarin
Study Initiator and Funder	Bayer AG, 51368 Leverkusen
Research question and objectives	
This population-based study will identify NVAf patients who initiate apixaban, rivaroxaban or warfarin as treatment for SPAF. We will compare safety and effectiveness using real world data from routine general practice in the UK, using The Health Improvement Network (THIN). Primary Objectives
 
 • To compare the safety of rivaroxaban (20mg and 15mg; OD) and apixaban (5mg and 2.5mg; BID) vs warfarin in patients appropriately and inappropriately receiving standard and reduced doses of each NOAC in accordance with the label for SPAF. 
 ○ Intracranial hemorrhage (intracerebral hemorrhage, subarachnoid hemorrhage, subdural and epidural

	
hematoma)
 
 ○ Hemorrhagic stroke (intracerebral hemorrhage, subarachnoid hemorrhage) 
 • To compare the effectiveness of rivaroxaban (20mg and 15mg; OD) and apixaban (5mg and 2.5mg; BID) vs warfarin in patients appropriately and inappropriately receiving standard and reduced dose in accordance with the label for SPAF. 
 ○ Ischaemic Stroke and Systemic Embolism ○ Myocardial Infarction 
Secondary Objectives
 
 • To evaluate the outcomes in sub-group of patients with renal impairment and diabetes • To evaluate all-cause mortality in rivaroxaban and apixaban, as compared to warfarin • Drug utilisation and patient characterization of rivaroxaban, apixaban and warfarin receiving standard and reduced dose in accordance and not in accordance with the label • Drug utilisation/prescription behaviour and patient characterization following the first Intracranial haemorrhage or Ischaemic Stroke during the study period
Country(-ies) of study	United Kingdom
Author	
[Redacted]
 
[Redacted]
 
[Redacted]
 
[Redacted]
 
[Redacted]
 
[Redacted]
 
[Redacted]
 
[Redacted]
 
[Redacted]
 
[Redacted]
 
[Redacted]
 
[Redacted]
 
[Redacted]
 
[Redacted]
 
[Redacted]
 
[Redacted]

Marketing authorization holder

Marketing authorization holder(s)	Bayer AG, 51368 Leverkusen
MAH contact person	[REDACTED] [REDACTED] [REDACTED] [REDACTED] [REDACTED] [REDACTED]

The study will be conducted in compliance with the protocol and any applicable regulatory requirements.

Throughout this document, symbols indicating proprietary names (®, TM) may not be displayed. Hence, the appearance of product names without these symbols does not imply that these names are not protected.

1. Table of contents

Post Authorization Safety Study (PASS) Information	1
1. Table of contents	4
2. List of abbreviations	6
3. Responsible parties	7
3.1 Study initiator and funder	7
3.2 Collaborator(s)/External partner(s)/Committee(s)	7
4. Abstract.....	8
5. Amendments.....	12
6. Milestones	12
7. Rationale and background	13
8. Research questions and objectives	15
8.1 Primary objective.....	15
8.2 Secondary objectives	15
9. Research methods	16
9.1 Study design	16
9.1.1 Primary end-points	17
9.1.2 Secondary end-points	17
9.2 Setting.....	17
9.2.1 Study population	17
9.2.2 Study time frame	17

Rationale and background	
A recent cohort study in the UK showed that amongst patients with a history of NVAf using NOAC without an apparent indication for dose reduction, the reduced dose was prescribed in approximately 30% of patients receiving apixaban and 10% of patients receiving rivaroxaban in the new users of both-agents (Study 19330, unpublished data). We hypothesize that in real-world studies performed in the UK the high percentage of reduced dose apixaban use could translate into higher rates of stroke and systemic embolism than with rivaroxaban, which appears to be prescribed at reduced doses less frequently. On the other hand, patients with renal impairment receiving standard dose of NOAC are at increased risk of bleeding. Although, warfarin use has certainly decreased in the recent years, this drug remains the main oral anticoagulant used in the UK. It has also been the active comparator of choice in most clinical trials of NOAC (O'Dell et al.) and in our opinion constitutes an ideal reference drug for these analyses. Both the standard and the reduced dose of NOACs have been compared to warfarin in clinical trials and shown to be as safe and effective as warfarin. Warfarin itself does not have dose-reduction requirements however the dose needs to be adjusted to maintain INR between 2.0-3.0. Rivaroxaban and apixaban are most widely used NOACs in the UK whereas the use of dabigatran is low and declining since 2014 (Study 19330, unpublished data). Also, the appropriate and inappropriate use

	
of dabigatran is difficult to estimate due to a multiple criterion in the label for dose reduction which is difficult to assess using secondary data sources. Risk of major bleeding especially GI bleeding for NOACs is extensively studied, and our research question is to study the effect of under-dosing on the risk of stroke (effectiveness outcome). However, to also study the other side of the balance which is bleeding, we included ICH because it is an event comparable to stroke in terms severity. GI bleeding is an acute event, usually followed by complete recovery in vast majority of patients. Therefore, GI Bleeding is not included as an outcome in this study.
 
Regarding MI, results from the key trials are variable but shows protective effect of rivaroxaban. Therefore, it is important to further investigate MI as an outcome in a large population based cohort of patients.


Research question and objectives
	
This population-based study will identify NVAf patients who initiate apixaban, rivaroxaban or warfarin as treatment for SPAF. We will compare safety and effectiveness using real world data from routine general practice in the UK, using The Health Improvement Network (THIN).
 
Primary Objectives
 
 • To compare the safety of rivaroxaban (20mg and 15mg; OD) and apixaban (5mg and 2.5mg; BID) vs warfarin in patients appropriately and inappropriately receiving standard and reduced doses of each NOAC in accordance with the label for SPAF. 
 ○ Intracranial hemorrhage (intracerebral hemorrhage, subarachnoid hemorrhage, subdural and epidural hematoma) ○ Hemorrhagic stroke (intracerebral hemorrhage, subarachnoid hemorrhage) • To compare the effectiveness of rivaroxaban (20mg and 15mg; OD) and apixaban (5mg and 2.5mg; BID) vs warfarin in patients appropriately and inappropriately receiving standard and reduced dose in accordance with the label for SPAF. 
 ○ Ischaemic Stroke and Systemic Embolism ○ Myocardial Infarction 
Secondary Objectives

	
 • To evaluate the outcomes in sub-group of patients with renal impairment and diabetes • To evaluate all-cause mortality in rivaroxaban and apixaban, as compared to warfarin • Drug utilisation and patient characterization of rivaroxaban, apixaban and warfarin receiving standard and reduced dose in accordance and not in accordance with the label • Drug utilisation/prescription behaviour and patient characterization following the first Intracranial haemorrhage or Ischaemic Stroke during the study period

Study design
	
This is a population-based retrospective cohort study with a nested case-control analysis to assess safety and effectiveness of rivaroxaban and apixaban versus warfarin in a cohort of NVAF patients from THIN database in the UK.
 
The study period extends from 1st January 2012 up to last available database extraction (at time of writing, December 2017).
 
Among the THIN source population, three separate cohorts of new users of rivaroxaban, apixaban and warfarin (index drug) using the date of first prescription (start date) of the respective drug will be ascertained. Event date = index date for case-control analysis
 
This study will apply a new-users (initiators) design and will be further stratified as naïve and non-naïve users.

Population
	
Inclusion criteria
 
 • Patients aged ≥ 18 Years of age • NVAF • New users of Rivaroxaban, Apixaban, Warfarin • At least one year enrollment with the primary care physician (PCP) • One year since first health contact recorded in THIN prior to the first prescription of a study drug 
Exclusion criteria
 
 • Patients with other recent indications of OAC initiation as described in section 9.1. • Individuals on more than one OAC on the start date.

	
 • Users of Rivaroxaban apart from 15/20mg daily dose • Users of Apixaban apart from 5/10mg daily dose
Variables	
Detailed descriptive variables including baseline characteristics will be captured for the population, including co-medications and comorbidities at start date. Renal disease using estimated glomerular filtration rate (eGFR) as well as ACR (Albumin/Creatinine Ratio) where available will also be ascertained, as well as risk scores, lifestyle factors and healthcare utilization. Dose, posology, duration of study drugs and other anticoagulant on start date and thereafter will be ascertained.

Data sources	
THIN - The population included in THIN is representative of the UK as a whole in terms of age, sex and geographic distribution. THIN currently collects data from close to 500 practices, covering 6% of the general population of the UK population.

Study size	
Study 19330 (unpublished data) conducted in UK identified 8,629 initiators of apixaban and 12,353 initiators of rivaroxaban among patients with NVAf from 2011 through 2016 within the THIN database.

Data analysis	
Describe the three study cohorts i.e. patients prescribed with rivaroxaban, apixaban, warfarin by baseline characteristics, use of medications, comorbidities and healthcare utilization among the three study cohorts and contrast them with the baseline characteristics of patients in relevant, phase III clinical trials.
 
Two independent follow-ups will be performed, one for each analysis. Safety and Effectiveness: In this follow-up members of all three study cohorts will be followed from the day after start date up until the earliest of: a) first occurrence of Intracranial hemorrhage (intracerebral hemorrhage, subarachnoid hemorrhage, subdural and epidural hematoma), b) an ischemic event (Ischaemic Stroke /Systemic Embolism), c) Myocardial Infarction, d) death, and e) end of study period.
 
All-cause mortality: the follow-up of members of all three study cohorts will be followed from the day after start date up until the earliest of: a) date of death, and b) end of study period. The end of study period is defined as end of last data collection

	
in each practice.
 
Analyze safety, effectiveness, and all-cause mortality associated to use of the study drugs in three independent nested-case control analyses. Estimates for standard as well as for reduced dose of study drugs will be obtained. These three analyses will include all cases identified in each follow-up (respectively: intracranial hemorrhage events, ischemic events, and deaths) and an analysis-specific group of controls. These control groups will comprise a random sample of members of all three cohorts, frequency-matched by age, sex and calendar year to each set of cases. Under our study design of incidence density sampling, the odds ratio (OR) is an unbiased estimator of the incidence rate ratio (RR). Unconditional logistic regression models will be used to obtain OR estimates adjusted by baseline variables described above and OAC use at index date.
 
Outcomes will be analysed for the sub-group of NOAC users appropriately and inappropriately receiving standard and reduced dose. Outcomes will be analysed in the sub-group of diabetics and by renal function (CKD-EPI).
 
Further, the patterns of use of study medication before and after intracranial hemorrhage events, and ischemic events that occurred during the study period will be described.

Milestones	The project is planned to begin in December 2018 and will end in December 2019

5. Amendments

None

6. Milestones

Table 1: Milestones

Milestone	Planned date
Study Start	December 2018

Registration in the EU PAS register	December 2018
Study End	October 2019
Final report of study results	December 2019

7. Rationale and background

The prevalence of AF in England in 2016-17 was estimated to be 1.8% using Quality and Outcomes Framework (QOF) data (NHS Digital 2016). QOF is a voluntary incentive and reward system for general practice and includes an estimate of disease prevalence based on the number of patients with certain conditions, including AF, within practices lists. Other estimates based upon the GRASP (Guidance on Risk Assessment and Stroke Prevention) risk assessment tool of NHS Improvement estimates AF prevalence to be 1.76% (Cowan et al. 2013).

Bayer currently markets rivaroxaban in the UK which is indicated for the prevention of stroke and systemic embolism in adult patients with NVAF as well as the treatment and prevention of VTE. Other NOACs indicated for prevention of stroke and systemic embolism, include apixaban and dabigatran. In the UK, warfarin remains a widespread AF therapy although following the introduction of NOACs, its use in usual clinical practice has diminished significantly. Rivaroxaban was first marketed in 2008 in the UK, whereas apixaban was introduced in 2011. By choosing this study period, we ensure that all three study drugs were available throughout the study. Each individual NOAC licensed for the prevention of stroke in AF has different dosing recommendations and some anecdotal reports have previously indicated that there may be a clinically meaningful difference in the rates of lower doses of these agents as would be expected based on clinical trial data or the known prevalence of indications for reduced dose reflected in the respective drug labels.

The currently marketed NOACs have been extensively investigated in numerous post-marketing cohort studies. However, the methodologies employed and the sources of data adopted for these studies have been highly variable including data captured from both administrative databases as well as research databases. Previous work by Fay et al (Fay, Martins, and Czekay 2016) investigated the dosing patterns of NOACs for stroke prevention in AF using prescription data obtained from the UK, Germany and France. The outcomes indicated a greater use of lower doses of NOACs for AF therapy than were observed in the Phase III trials. Further work in the U.S. by Yao et al (Yao et al. 2017) has investigated dosing of NOACs in a large administrative database and the associated outcomes of patients administered lower doses of these agents with respect to stroke and major bleeding in patients with or without renal dysfunction. Those patients with no renal indication for dose reduction were potentially under dosed and this was associated with a higher risk of stroke but no significant difference in major bleeding. Of interest, potential under dosing with apixaban was associated with higher rates of stroke and systemic embolism compared to the standard dose whilst there was no significant difference between the reduced dose and standard dose with respect to rivaroxaban. A limitation of this study was the inability to account for other factors associated with

dose reduction for apixaban, a limitation which may be overcome by using the THIN database and consequently better reflecting the appropriate use of these agents in usual clinical practice.

Bayer has recently conducted a retrospective cohort study on prescription patterns of NOACs in NVAF patients in UK general practice using a combination of the THIN and CPRD databases. Amongst patients without an apparent indication for dose reduction, the reduced dose was prescribed in approximately 30% of patients receiving apixaban and 10% of patients receiving rivaroxaban in the new-users of both agents (Study 19330, unpublished data). We therefore hypothesize that in the UK, the higher than expected rates of reduced dose apixaban use as compared to the Phase III trials will exhibit higher rates of stroke and systemic embolism versus warfarin than rivaroxaban, which appears to be prescribed at the reduced dose less frequently. Also, patients with renal impairment receiving standard dose are at increased risk of bleeding. Although, warfarin use has certainly decreased in the recent years, this drug remains the main oral anticoagulant used in the UK. It has also been the active comparator of choice in most clinical trials of NOAC (O'Dell et al.) and in our opinion constitutes an ideal reference drug for these analyses. Both the standard and the reduced dose of NOACs have been compared to warfarin in clinical trials and shown to be as safe and effective as warfarin. Warfarin itself does not have dose-reduction requirements however the dose needs to be adjusted to maintain INR between 2.0-3.0. Rivaroxaban and apixaban are most widely used NOACs in the UK whereas the use of dabigatran is low and declining since 2014 (Study 19330, unpublished data). Also, the appropriate and inappropriate use of dabigatran is difficult to estimate due to a multiple criterion in the label for dose reduction which is difficult to assess using secondary data sources. Risk of major bleeding especially GI bleeding for NOACs is extensively studied, and our research question is to study the effect of under-dosing on the risk of stroke (effectiveness outcome). However, to also study the other side of the balance which is bleeding, we included ICH because it is an event comparable to stroke in terms severity. GI bleeding is an acute event, usually followed by complete recovery in vast majority of patients. In terms of the balanced outcomes, it is important to take account of the severity of the disease events prevented and caused by the intervention, and not just the frequencies of the events. Thus GI bleeds, which are sometimes severe, are acute events usually followed by recovery without sequelae, while strokes and ICH can leave residual physical and/or cognitive impairments in those who survive, and may require complex and lifelong interventions. Therefore, GI Bleeding is not included as an outcome in this study.

Regarding MI, here are some of the results from the key trials:-

- Chatterjee et al reported (2013) that rivaroxaban was associated with a reduction in MI across ATLAS EINSTEN RECORD and ROCKET trials (OR in ROCKET AF was 0.8 (0.61-1.04)).
- Pioneer indicated high rates coronary revascularization in AF patients with CAD (20-45%) but major adverse CV event (CV death, MI, stroke) were similar to VKA at both doses of rivaroxaban.

- Results of ATLAS ACS TIMI 46 suggested that rivaroxaban may meaningfully reduce major CV events with an acceptable incremental bleeding profile. In ATLAS ACS 2 TIMI 51 the 5mg dose was observed to reduce the rate of MI versus placebo although this dose level did not reduce death from cardiovascular causes.
- Danish registry (Lee 2018) observed that NOACs were associated with a significant reduction of MI compared with VKA – the highest absolute risk difference was observed between rivaroxaban and VKA

Therefore, it is important to further investigate MI as an outcome in a large population based cohort of patients.

Further, it is important to understand how are the OACs used after a patient experiences an event on the index OACs for e.g. major bleeding or stroke.

This will be the first study which will evaluate the safety and effectiveness of rivaroxaban and apixaban compared to warfarin in patients appropriately and inappropriately receiving standard and reduced doses of each NOAC in accordance with the label in a large-population based cohort of NVAf patients.

8. Research questions and objectives

This population-based study will identify NVAf patients who initiate apixaban, rivaroxaban or warfarin as treatment for SPAF. We will compare safety and effectiveness using real world data from routine general practice in the UK, using The Health Improvement Network (THIN).

8.1 Primary objective

- To compare the safety of rivaroxaban (20mg and 15mg; OD) and apixaban (5mg and 2.5mg; BID) vs warfarin in patients appropriately and inappropriately receiving standard and reduced doses of each NOAC in accordance with the label for SPAF.
 - Intracranial hemorrhage (intracerebral hemorrhage, subarachnoid hemorrhage, subdural and epidural hematoma)
 - Hemorrhagic stroke (intracerebral hemorrhage, subarachnoid hemorrhage)
- To compare the effectiveness of rivaroxaban (20mg and 15mg; OD) and apixaban (5mg and 2.5mg; BID) vs warfarin in patients appropriately and inappropriately receiving standard and reduced dose in accordance with the label for SPAF.
 - Ischaemic Stroke and Systemic Embolism
 - Myocardial Infarction

8.2 Secondary objectives

- To evaluate the outcomes in sub-group of patients with renal impairment and diabetes
- To evaluate all-cause mortality in rivaroxaban and apixaban, as compared to warfarin

- Drug utilisation and patient characterization of rivaroxaban, apixaban and warfarin receiving standard and reduced dose in accordance and not in accordance with the label
- Drug utilisation/prescription behaviour and patient characterization following the first Intracranial haemorrhage or Ischaemic Stroke during the study period

9. Research methods

9.1 Study design

This is a population-based retrospective cohort study with a nested case-control analysis to assess safety and effectiveness of new users of rivaroxaban and apixaban versus new users of warfarin in a cohort of NVAF patients from THIN database (secondary data) in the UK.

All patients aged 18 and above and who have been enrolled in the databases for at least 1 year and had their first prescription recorded in the databases at least 1 year ago will be included in source population. A patient will be considered eligible to enter a study cohort as a new-user of one of the three study drugs when he or she has a first prescription of the index drug recorded during the enrollment period. Individuals meeting the criteria of new user of more than one study drug during the enrollment period will be assigned to the study cohort with the earliest start date. Among the three study cohorts, we will further identify patients with Non-valvular Atrial Fibrillation (NVAF) defined as: Patients with a record of Atrial fibrillation (AF) any time prior start date or within the 2 weeks after the start date, and free of valvular replacement or mitral stenosis prior to start date or 2 weeks after start date.

Additionally, NVAF patients with other recent indications of OAC initiation will be excluded. Thus patients with an entry of venous thromboembolism or orthopedic arthroplasty recorded in the last 3 months before the date of first time use of OAC or in the week after the start date will be excluded from the study cohort. Individuals on more than one OAC on the start date will also be excluded.

The validity of a nested case-control (NCC) study that follows the incidence-density based NCC paradigm is equivalent to the corresponding cohort study. NCC is simply described as an efficient person-time sampling strategy to obtain the same results as in a cohort study. In this study, this efficiency gain is quite substantial. It is quite common that daily-dose of these drugs changes during follow-up time. As described in the section 9.3.1.1, the algorithm to be used to ascertain daily dose at one specific time-point (one unit of person-time) is already quite complex. An attempt to classify the daily dose of every single unit of person-time of follow-up for the entire cohort would be not only be time-consuming but also prone to misclassification. The reason is that the algorithm is not entirely automated but requires some fine tuning based on recent prescription history. Thus, using a NCC approach enables us to minimize misclassification using all available information to estimate the daily-dose at the two most important time points: a) at index date (date of the event among cases or random date among controls) and b) at start date.

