9.2.3 Selection criteria

Inclusion criteria

- Patients aged ≥ 18 years of age
- NVAf
- New users of Rivaroxaban, Apixaban, Warfarin
- At least one year enrollment with the general practice (GP)
- One year since first health contact recorded in THIN prior to the first prescription of a study drug

Exclusion criteria

- Patients with other recent indications of OAC initiation as described in section 9.1.
- Individuals on more than one OAC on the start date.
- Users of Rivaroxaban apart from 15/20mg daily dose
- Users of Apixaban apart from 5/10mg daily dose

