9.3 Variables

9.3.1 Exposure definition

Among the source population resulting from the THIN database, we will ascertain three separate/mutually exclusive cohorts of new-users of rivaroxaban, apixaban and warfarin (index drug) using the date of first prescription (start date) among the three study drugs. Index date= event date in the nested case-control analysis.

This study will apply a new-users (initiators) design (Ray 2003) and then further stratify the new users into naïve and non-naïve. A patient is considered eligible as new user of rivaroxaban, apixaban or warfarin if he or she had a first prescription of the respective drug recorded during the enrolment period and never received one prior for that index OAC. Further, naïve users are individuals with no previous recorded use of any OAC in the database before the start date. Non-naïve patients are those with one or more oral anticoagulant prescriptions other than the index drug recorded before the start date.

The study drug will be further stratified to Current, recent, past and non-use specified in [section 9.3.3](#)

Among cases of intracranial haemorrhage or ischemic events during the study period, use of the study drugs after index date (index date=event date in the nested case-control analysis) will also be ascertained within one year after the index date.

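### The 3-month look-back for other OAC indications runs from first OAC use, not the start date, so in non-naïve patients it misses recent events and excludes for old ones

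*Protocol*

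**What the plan says.** Section 9.1 gives the purpose of the rule: "NVAF patients with other recent indications of OAC initiation will be excluded". It then makes the rule operational through a VTE or orthopaedic arthroplasty entry "recorded in the last 3 months before the date of first time use of OAC or in the week after the start date". The selection criteria in 9.2.3 add no dates of their own and point back: "Patients with other recent indications of OAC initiation as described in section 9.1".

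Section 9.3.1 builds the cohorts "using the date of first prescription (start date) among the three study drugs". A new user is defined drug by drug, as someone who "never received one prior for that index OAC". Earlier use of a different OAC is therefore allowed: "Non-naïve patients are those with one or more oral anticoagulant prescriptions other than the index drug recorded before the start date". There is no time limit on the history searched, since "naïve users are individuals with no previous recorded use of any OAC in the database before the start date".

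The valve criterion in 9.1 uses the start date on both sides: "free of valvular replacement or mitral stenosis prior to start date or 2 weeks after start date". The AF criterion in the same sentence does so too.

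**The concern.** One sentence uses two anchor dates. In a naïve patient, first OAC use and the start date are the same day, so the difference has no effect. In a non-naïve patient, first OAC use comes before the start date, possibly by years. The look-back then examines the wrong period. It says nothing about the months before the study drug was started, and it excludes for events that may be long past.

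The study concerns stroke prevention in AF, and section 7 notes that rivaroxaban is also indicated for VTE. A patient with AF who starts a study drug just after a new VTE or joint replacement is the kind of patient the rule is meant to remove. If kept, that patient can enter the case-control analyses. In the dose analysis of 9.7 (a), the dose would be labelled appropriate or inappropriate against criteria written for stroke prevention. Section 9.7 (d) also analyses non-naïve patients separately, and there no naïve patients dilute the error.

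**Working it through.** No sample-size or power figure is involved, and the plan gives no number to reproduce. The check applies the rule as written, and with the look-back moved to the start date, to example patients.

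**Inputs**

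- F = date of first OAC use; S = start date (first prescription of the index study drug, 9.3.1); E = date of the VTE or arthroplasty entry.
- 3 months is taken as 91 days, and the week after start as S to S + 7 days.
- The patient dates are illustrative and are not in the protocol.

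**Rules**

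- As written: exclude if F − 91 ≤ E ≤ F, or S ≤ E ≤ S + 7.
- Start-date anchor: exclude if S − 91 ≤ E ≤ S + 7.

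If F = S (naïve), the two rules are identical. If F < S (non-naïve), the rule as written never excludes for an event with F < E < S, however close E is to S.

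| Patient | F | E | S | E to S | As written | Start-date anchor |
|---|---|---|---|---|---|---|
| Naïve, VTE before start | 1 Jun 2014 | 2 May 2014 | 1 Jun 2014 | 30 days | excluded | excluded |
| Non-naïve, VTE before start | 1 Mar 2005 | 2 May 2014 | 1 Jun 2014 | 30 days | **kept** | excluded |
| Non-naïve, arthroplasty before start | 1 Jan 2011 | 1 Jan 2016 | 1 Mar 2016 | 60 days | **kept** | excluded |
| Non-naïve, VTE just after start | 1 Mar 2005 | 4 Jun 2014 | 1 Jun 2014 | −3 days | excluded | excluded |
| Non-naïve, VTE before first OAC only | 1 Mar 2005 | 30 Jan 2005 | 1 Jun 2014 | 9.3 years | **excluded** | kept |
| Non-naïve, OAC begun for VTE, early switch | 8 Oct 2011 | 1 Oct 2011 | 1 Mar 2012 | 152 days | excluded | kept |

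Rows 2 and 3 show the gap just before the start date. Row 5 shows exclusion for an event that is not recent. Row 6 is taken up under the objection.

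**How old an excluding event can be.** Section 9.4 dates THIN from 2002, and 9.2.2 takes the data to December 2017. From 1 January 2002 to 31 December 2017 is 16.0 years. An older event could count only if earlier records are held, which the protocol does not say.

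**Which cohorts.** All three can contain non-naïve patients. An earlier warfarin user can enter a NOAC cohort but never the warfarin cohort, because a new user must not have had the index drug before. A non-naïve warfarin starter needs earlier use of some other OAC. This suggests that most affected patients are NOAC starters, but the protocol gives no count.

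**Scale, illustration only.** Section 9.5 reports 8,629 + 12,353 = 20,982 NOAC initiators in Study 19330. Assume that 30% to 50% are non-naïve and that 1% to 3% of those have an event in the gap; neither share is in the protocol. Then 20,982 × 0.30 × 0.01 ≈ 63 and 20,982 × 0.50 × 0.03 ≈ 315, or 0.3% to 1.5% of NOAC initiators. Wrongly excluded patients would be additional. This shows scale under those assumptions and is not an estimate.

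**The case against.** **The anchor may be deliberate.** Tying the look-back to first OAC use removes patients whose anticoagulation was begun for VTE or surgery. Row 6 shows that a plain swap of anchors would admit someone who began warfarin for a VTE and switched five months after the event. This stands, and it shapes the fix. It does not rescue the rule as written, which still misses new events just before the start date and has no limit that would keep the excluding event recent.

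**The phrase may loosely mean first use of the index OAC.** The protocol is loose with date labels elsewhere: Table S1 in Annex 3 defines NVAF around the index date where 9.1 uses the start date. But the sentence at issue uses the start date as a separate term, so the literal reading is the natural one. If the looser meaning was intended, the text still needs correcting, because a programmer following it would code a different date.

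**The effect is contained.** Section 9.7 repeats the analyses separately in naïve and non-naïve patients, and naïve status is among the covariates. The naïve stratum is clean. Stratifying or adjusting does not remove ineligible patients from the non-naïve stratum.

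**The dose exclusions already remove some of these starts.** Under 9.3.1.1, some 15 mg rivaroxaban prescriptions are assigned two tablets a day, giving 30 mg, which 9.2.3 excludes. The cover is partial: starts at the retained daily doses of rivaroxaban or apixaban stay in, and no such exclusion applies to warfarin.

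**The bias is not shown.** A reader might infer that contaminated NOAC cohorts are being compared with a clean warfarin cohort. The documents do not support that. Non-naïve warfarin starters share the gap, and the main comparisons in 9.7 classify current use at the index date, not the starting cohort. Every patient also has recorded AF, so an intervening VTE or arthroplasty was not necessarily the reason for treatment.

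**Conclusion.** The point holds as a defect in a stated eligibility rule. In non-naïve patients, the look-back in 9.1 read literally keeps those with a VTE or arthroplasty between first OAC use and the study-drug start, and excludes others for events that may be years old. Both results defeat the aim of removing recent other indications, and neither 9.2.3 nor 9.3.1 corrects them. Only the look-back is affected; the week after the start date is correctly anchored, and naïve patients are classified as intended.

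The size cannot be computed from the protocol, which gives neither the non-naïve share nor the frequency of such events. A concentration on the NOAC side is probable from the new-user definition but is an inference. Two stronger claims should not be made. Exclusion for events decades old goes beyond the roughly 16 years that the stated dates allow. A bias of known direction or amount in the primary odds ratios has not been demonstrated. The conclusion rests on the literal reading of first OAC use.

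**What to change.** In 9.1, and through it 9.2.3, exclude patients with VTE or arthroplasty recorded from 3 months before to 1 week after the start date of the index study drug, for naïve and non-naïve patients alike.

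Decide separately whether patients whose earlier OAC was begun for VTE or arthroplasty should also be removed. If so, write that as its own criterion, with its own anchor and time limit, so that the case in row 6 is handled on purpose and not as a side effect of the look-back date.

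The cost is one phrase in the protocol and one date variable in the extraction code, plus a second criterion if wanted. No new data are needed. Cohort counts would change slightly, so the change should be made before the cohorts are extracted.
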